Islahul Qulub: Islamic Trauma Healing. Several years of iterative, collaborative development work with the Somali community have guided the content and format of the Islamic Trauma Healing program. A manual for the program was developed (Lang, Zoellner, Graham, Marks, & Feeny, 2016), and a local Imam carefully reviewed the content of the manual. Focus group feedback from lay leaders and group members was also utilized in revisions. The program was designed for groups of 5-7 members, with two lay leaders of the same gender. The program is structured so that the lay leader training, comprised of two 4-hour trainings, focuses on teaching lay leaders the skills of discussion leading, with the manual content providing more of the direct therapeutic work. That is, the lay leaders are not explicitly taught how to be psychotherapists or how to do cognitive behavioral therapy specifically. The manual contains an introduction to trauma healing, including a description of types of trauma exposure and common reactions, as well as Islamic principles related to trauma healing. Session-by-session content is clearly spelled out in the manual. Each session includes time for community building rituals (e.g., sharing tea or coffee), spiritual preparation using a brief supplication written by the local Imam, prophet narratives relevant to trauma healing, and a brief closing supplication also written by the Imam. In the first session, a rationale for the program, common reactions to trauma, and a breathing relaxation exercise are described. Starting in the second session and continuing through the last session, talking individually to Allah about the trauma is conducted. In the last session, group members are encouraged to organize a closing event at which certificates of program completion are given.

The program is 6 sessions long. This duration is in line with evidence that very brief or shortened protocols (e.g., four 30 min sessions) can substantially reduce PTSD symptoms (Cicrang et al., 2011; van Minnen & Foa, 2006). Key components of the program are prophet narratives aimed at targeting trauma-

related beliefs, and talking to Allah, aimed at targeting trauma memories.

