F. Power Analysis

We estimated sample size based primarily on Specific Aim 1. We estimated power to detect effects using G*Power and Optimal Design (for multilevel data), with $\alpha = .05$ and power $(1 - \beta) = .80$, completing 10,000 replications per analysis. With a conservative estimated dropout of 20% across conditions, though no dropout occurred in our pilot work, we will have power to detect moderate to large effects of condition on outcomes at post-treatment ($d = 0.72$) with 30 per group, and ($f^2 = 0.28$) with generalized linear models (GLM),

both large effects. For repeated measures analyses, with 4 data points, 30 per group with 20% missing data, we will be able to detect medium effects ($d = 0.60$) on change over time. These effect sizes are well below the observed effects in our pilot work ($g = 0.76$ to $g = 3.22$). For Specific Aim 2, the same power calculations for Aim 1 apply; however, tests of indirect effects are exploratory, we will be powered to detect a moderate indirect effect ($a*b = 0.25$), using the same constraints as above. To balance feasibility and ability to detect meaningful effects, we will recruit 30 individuals per treatment group

G. Analytic Strategy

Data will be screened for accuracy, missing values, and fit between the data and the assumptions of the general linear and linear mixed-model analysis (e.g., linearity, multivariate normality, independence of errors; Tabachnick & Fidell, 2007). Data transformations or model respecifications will be performed for any violated assumptions. We will implement pattern-mixture models to examine whether the missingness can be considered ignorable. For non-ignorable missing data, values will be multiply imputed and data recombined using Rubin's rules (Rubin, 1987) in the mixed model program. We will examine associations between primary dependent variables and factors such as gender, age, time since trauma, etc. and make appropriate analytic adjustments. We will test all covariate by predictor interactions to ensure our main effects are independent of the level of these putative covariates; these tests of effect modification are easily accommodated. However, we are underpowered to assess these interactions. To account for subjects being nested within groups in the treatment condition, we will co-vary treatment group using dummy codes in all analyses, as linear mixed models are difficult to estimate when the number of clusters is very small (Snijders, 2005).

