Specific Aim 1: Therapeutic Effects

Hypothesis: Those in Islamic Trauma Healing will show a greater reduction of PTSD symptoms and related psychopathology than those in the waitlist condition (WL).

Predictor Variables: Predictor is treatment (Islamic Trauma Healing vs. WL)

Dependent Variables: PTSD severity (PS-SR-5, primary outcome), depression (PHQ-9), somatic symptoms (PHQ-15), and well-being (WHO-5) will be measured.

Analyses: Because of the presence of clustering (participants in groups, observations over time, and participants in random assignment clusters), we will use generalized linear mixed models (GLMMs), which can account for the presence of clustering in data with varying distributional forms. We will compare pre-post GLMMs with those using data from all four time points to estimate the effects of treatment on both the level of the outcome at post-treatment, as well as change over time. To account for clustering (in treatment groups and random assignment clusters), we will include random intercepts for both treatment group and cluster (for those choosing to be randomized in a cluster). Because the waitlist control and non-clustered individuals will *not* be in a cluster, we will use the method outline by Sterba and Bauer (2008) to model random intercepts for *only* those in treatment or a cluster, and test whether modeling residuals as a function of clustering status appropriately models heteroskedasticity of residuals across clustering status. To test models of change over time, these models would be extended to three level models, with random intercepts and random coefficients for time-varying covariates (e.g., time) specified at Level 2 if the model fit is better than a fixed effects model.

Dropout. We will compare the percent of those who drop out of Islamic Trauma Healing to WL using a chi-square test. Reasons for dropout will be documented and compared across groups. Psychopathology and functioning of dropouts will be compared, using chi-square or *t*-tests, as appropriate.

Satisfaction. Means and standard deviation of satisfaction (CSQ) will be reported. A comparison to WL does not make sense, as there are no services with which to compare.

Specific Aim 2: Potential Mediators Change with Active Intervention

Hypothesis: Those in Islamic Trauma Healing will show a greater reduction of negative beliefs (PTCI), connectedness (SC; DSES), and/or forgiveness (TRIM-R) than those in the waitlist condition (WL).

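### The post-treatment detectable effect of d = 0.72 matches a calculation on independent people and states no clustering inputs; two-sided with the stated dropout it is about 0.83, and larger once therapy groups are counted

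*Combined protocol and SAP*

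**What the plan says.** Section F (Power Analysis) sets alpha at .05 and power at .80. It names its tools: "We estimated power to detect effects using G*Power and Optimal Design (for multilevel data"). It allows for attrition: "With a conservative estimated dropout of 20% across conditions, though no dropout occurred in our pilot work". On that basis it claims that "we will have power to detect moderate to large effects of condition on outcomes at post-treatment". The result is given for "outcomes at post-treatment ($d = 0.72$) with 30 per group", and the section closes with the decision that "we will recruit 30 individuals per treatment group". It adds a repeated-measures figure of d = 0.60, and tells the reader that these effects are comfortably smaller than those seen in the pilot, g = 0.76 to 3.22. It reports no ICC, number or size of therapy groups, size of randomisation unit, design effect, sidedness or baseline correlation.

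Specific Aim 1 (Analyses) starts from the opposite premise: "Because of the presence of clustering (participants in groups, observations over time, and participants in random assignment clusters"). It fits random intercepts for both therapy group and randomisation unit. Section D (Procedures) lets up to three people be randomised together. Section B (Materials) fixes the scale of the therapy groups: "The program was designed for groups of 5-7 members".

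Section G (Analytic Strategy) gives a different method. Therapy group is entered as dummy codes in every analysis, on the ground that mixed models are hard to estimate with so few clusters.

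**The concern.** The sample size rests mainly on Aim 1, and the Aim 1 model treats participants as correlated within therapy groups and within randomisation units. For the same test and the same number of completers, any positive correlation of this kind makes the smallest detectable effect larger than it would be for independent people. A figure that already agrees with an independent-person calculation therefore gives the reader no sign that clustering was counted.

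Two things are at stake. If 80% power at d = 0.72 is not available, a null result could be read as stronger evidence of no effect than it is. And the reassurance that the detectable effects sit well under the pilot effects may fail at the lower end of the pilot range. Section F carries the same power calculations over to Aim 2, so the problem is not confined to the primary outcome.

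**Working it through.** **Inputs from the documents.** Alpha .05, power .80, 30 recruited per arm, 20% dropout (30 × 0.8 = 24 per arm), stated d = 0.72 (Section F); groups of 5 to 7 (Section B), so 30/7 ≈ 4.3 to 30/5 = 6 groups in the active arm; units of one to three people (Section D).

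**Assumptions, not in the documents.** Therapy-group ICC 0.05 to 0.20; five groups as the central case (24/5 = 4.8 completers each); unit ICC; baseline correlation. Total variance is 1.

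**Step 1: reproduce 0.72.** For independent people, d = (z_α + z_power) × √(2/n); the t values come from the noncentral t.

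| Case | Normal | t | Power at 0.72 (t) |
|---|---|---|---|
| Two-sided, n = 30 | 2.802 × √(2/30) = 0.723 | 0.736 | 78.3% |
| One-sided, n = 24 | 2.486 × √(2/24) = 0.718 | 0.729 | 79.2% |
| Two-sided, n = 24 | 2.802 × √(2/24) = 0.809 | 0.826 | 68.5% |

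The first two rows reproduce the plan's figure; neither contains clustering. The third row, two-sided with the stated dropout, does not reproduce it. Its 0.826 already exceeds the lowest pilot effect, 0.76.

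**Step 2: add therapy-group clustering in the active arm only.** With n = 24, m = 4.8 and k = 5:

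v1 = [1 + (m − 1) × ICC]/n; v2 = 1/n; SE = √(v1 + v2).

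Satterthwaite df = (v1 + v2)² / [v1²/(k − 1) + v2²/(n − 1)].

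At ICC 0.05: 1 + 3.8 × 0.05 = 1.19, so v1 = 1.19/24 = 0.0496, v2 = 0.0417, SE = 0.302, df = 12.1. At ICC 0.20: 1 + 3.8 × 0.20 = 1.76, SE = √(2.76/24) = 0.339, df = 9.3. Solving the noncentral t for 80% two-sided power:

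| ICC | d, df 46 | Power at 0.72 | d, Satterthwaite | Power at 0.72 |
|---|---|---|---|---|
| 0.05 | 0.86 | 65% | 0.92 | 59% |
| 0.10 | 0.90 | 61% | 0.97 | 55% |
| 0.20 | 0.97 | 55% | 1.06 | 48% |

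With Satterthwaite df and ICC 0.05 to 0.20, four groups give 0.97 to 1.17 and six groups 0.90 to 1.00.

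**Step 3: split the gap.** From 0.72 to 0.826 is about 0.11 and owes nothing to clustering; it reflects dropout or sidedness. Therapy-group clustering then adds 0.04 to 0.14 (df 46) or 0.10 to 0.24 (Satterthwaite).

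**Step 4: randomisation units.** Adding (u − 1) × ICC_u to the variance factor of both arms, with Satterthwaite df: units of 2 at ICC_u 0.05 give 0.95 to 1.09; units of 3 at ICC_u 0.10 give 1.03 to 1.15.

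**Step 5: baseline adjustment.** Multiply SE by √(1 − r²). At r = 0.5 the factor is 0.866. Without clustering, 0.826 × 0.866 = 0.715. With therapy-group ICC 0.05 to 0.20 and no unit term, d is 0.75 to 0.84 (df 46) or 0.80 to 0.92 (Satterthwaite).

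**The case against.** The strongest reply is that the documents do not show that clustering was left out. A multilevel power tool is named, neither sidedness nor baseline correlation is stated, and the planned pre-post models use baseline data. A two-sided figure of 0.72 that includes both dropout and therapy-group clustering is possible if an unstated baseline correlation was used: about 0.55 to 0.67 with df 46, or 0.62 to 0.74 with Satterthwaite df, at ICC 0.05 to 0.20. This stands. A reader might infer that the figure cannot contain any clustering allowance; that does not follow. What can be said is that none is reported and that simple independent-person calculations account for the figure.

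A reader might also infer that the design detects 0.92 to 1.06 instead of 0.72, and that clustering explains the difference. The documents support neither. That range needs assumed ICCs, five groups, two-sided testing, no baseline adjustment and small-sample df, and it has no randomisation-unit term. Part of the gap is dropout or sidedness.

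It is also fair that the calculation fits the random-intercept model of Aim 1 and not the dummy codes of Section G, and that this is a small trial whose size was chosen partly for feasibility. Neither point makes 0.72 checkable as printed.

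**Conclusion.** The point holds as a gap in the justification of the power figure. Without baseline adjustment, 0.72 is an independent-person value that is either two-sided without the stated dropout or one-sided with it. Two-sided with the dropout, the figure is about 0.83 before any clustering, and this rests only on the plan's own inputs plus two-sided testing and no baseline adjustment.

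Beyond that, size depends on assumptions the plan should supply. With five groups and therapy-group ICC 0.05 to 0.20, d is about 0.86 to 1.06 across the two df choices, with power at 0.72 of about 65% down to 48%. Randomisation units push it up; a baseline correlation of 0.5 brings the therapy-group range down to about 0.75 to 0.92. Most of these values lie above the lowest pilot effect of 0.76, so the general statement that the detectable effects fall well short of the pilot effects is not supported at the lower end. Nothing here shows that N = 60 is wrong for a small trial. A correction is advisable because the sample-size argument relies on this number.

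**What to change.** Keep N = 60 and revise the text of Sections F and G.

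- Restate the post-treatment detectable effect, and recompute the d = 0.60 repeated-measures figure, for the model actually planned.
- Write out sidedness, dropout, number and size of therapy groups, therapy-group ICC, unit size and ICC, baseline correlation and the df method. Where a value is assumed, show a range.
- Replace the comparison with the pilot effects by one that is true at their lower end.
- Reconcile the dummy codes of Section G with the random intercepts of Aim 1, and base the calculation on the method kept.

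The cost is rewording and a short recalculation, with no added participants. The downside is that the stated figures become less favourable.

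### The GLM figure f² = 0.28 does not match the 1-df treatment test it is attached to, and the detectable d = 0.72 is not well below the lowest pilot effect

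*Combined protocol and SAP*

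**What the plan says.** Section F bases the sample size on the first aim ("We estimated sample size based primarily on Specific Aim 1") and carries it over to the second ("For Specific Aim 2, the same power calculations for Aim 1 apply"). It sets α = .05 and power .80, without giving sidedness. "With a conservative estimated dropout of 20% across conditions", it claims moderate to large detectable "effects of condition on outcomes at post-treatment ($d = 0.72$) with 30 per group, and ($f^2 = 0.28$) with generalized linear models (GLM"), and then describes both as large. For repeated measures it adds that "we will be able to detect medium effects ($d = 0.60$) on change over time". It concludes: "These effect sizes are well below the observed effects in our pilot work ($g = 0.76$ to $g = 3.22").

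Under Specific Aim 1 the predictor is a single two-level factor: "Predictor is treatment (Islamic Trauma Healing vs. WL").

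Section F does not give the numerator df or number of predictors behind f² = 0.28, the analysed N, a baseline correlation or an ICC. It does not say which pilot outcome or contrast produced g = 0.76.

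**The concern.** Section F attaches d = 0.72 and f² = 0.28 to the same thing: the effect of condition at post-treatment, under one α, power, sample size and dropout rate. For two equal arms without adjustment, f² = d²/4, so d = 0.72 corresponds to f² = 0.13, less than half of 0.28. That gap raises the question of which test 0.28 belongs to.

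The pilot comparison raises a second question. It is worded as covering all the detectable effects, yet the post-treatment d and the smallest pilot effect are almost equal.

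At stake is whether a reader can verify the case for 30 per arm, which serves both aims, and whether the stated margin over the pilot effects is real.

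**Working it through.** **Inputs from the documents.** α = .05, power .80, 30 per arm, 1:1 allocation, 20% dropout (section F and section A). Analysed: 30 × 0.8 = 24 per arm, N = 48. One two-level predictor, hence 1 df (Specific Aim 1). Therapy groups of 5–7 members (section B).

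**Assumptions (not in the documents).** Therapy-group ICC 0.05 to 0.10; group size 6 before dropout, so m = 6 × 0.8 = 4.8; baseline correlation r.

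**1. The plan's d = 0.72 (noncentral t).** Several readings come close to it:

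| Reading | Detectable d |
|---|---|
| Two-sided, 30 per arm, no dropout | 0.74 (0.72 by normal approximation) |
| One-sided, 24 per arm | 0.73 (0.72 by normal approximation) |
| Two-sided, 24 per arm, unadjusted | 0.83; power at d = 0.72 is 68.5% |
| Two-sided, 24 per arm, r = 0.5 | 0.83 × √(1 − 0.25) = 0.72 |

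The figure can be reached, so it is not called an arithmetic error. The text does not say which reading was used.

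**2. The plan's f² = 0.28 (noncentral F, λ = f² × N).**

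| Test | N = 48 | N = 60 |
|---|---|---|
| 1 df, detectable f² | 0.171 | 0.135 |
| 1 df, eight predictors in the model | 0.172 | 0.136 |
| 1 df, power at f² = 0.28 | 94.8% | 98.1% |
| 4 df, detectable f² | 0.277 | 0.217 |
| 5 df, detectable f² | 0.304 | 0.237 |

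The stated figure does not reproduce as a 1-df test of treatment at either N. It matches a 4-df test at N = 48 numerically, but the documents give no origin for it.

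**3. Adding clustering.** With therapy groups in the active arm only, the design effect on the treatment contrast is (2 + (m − 1) × ICC)/2.

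- ICC 0.05: (2 + 3.8 × 0.05)/2 = 1.095; f² = 0.171 × 1.095 = 0.187.
- ICC 0.10: (2 + 3.8 × 0.10)/2 = 1.19; f² = 0.171 × 1.19 = 0.203.
- To reach 0.28 on 1 df: design effect 0.28/0.171 = 1.64, so ICC = (2 × 1.64 − 2)/3.8 = 0.34.

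On the d scale, two-sided with 24 per arm and r = 0.5, detectable d = 0.716 × √1.095 = 0.75 at ICC 0.05 and 0.716 × √1.19 = 0.78 at ICC 0.10.

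**4. Margin below the smallest pilot effect.**

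- d = 0.72: 0.76 − 0.72 = 0.04; 0.04/0.76 = 5%.
- d = 0.60: 0.76 − 0.60 = 0.16; 0.16/0.76 = 21%.
- Two-sided, unadjusted, 24 per arm: 0.83, which is above 0.76.

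**The case against.** **Different models.** The conversion f² = d²/4 holds only without adjustment. The GLMs described under Specific Aim 2 control for baseline, so a raw d and a partial f² need not convert. This stands: a baseline correlation of √(1 − 0.1296/0.28) = 0.73 would bring the two figures into line. It does not rescue 0.28 as the detectable effect, because the 1-df detectable partial f² stays near 0.17 whatever the correlation.

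**Possible clustering allowance.** Section F says that software for multilevel data was used, so some allowance may be built in. This also stands. An ICC of about 0.34 together with r = 0.73 would make both figures describe one 1-df effect. That ICC is large and neither value is stated, so the gap is one of reporting and 0.28 is not proved wrong.

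**A stronger reading to avoid.** Section G says "we will co-vary treatment group using dummy codes in all analyses". A reader might infer that 0.28 is a joint test of four group dummies, that the GLM therefore needs d = 2√0.28 = 1.06, and that the trial is badly underpowered. The documents do not support this. Thirty people in groups of at most 7 need at least five groups (30/7 = 4.3), and a 5-df test gives 0.304 at N = 48 or 0.237 at N = 60, neither of which is 0.28. Specific Aim 1 also models therapy group with random intercepts.

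**Wording of the pilot comparison.** The sentence directly follows d = 0.60, and how far below counts as well below is partly judgement. But its subject is plural, so 0.72 is naturally included, and a 5% margin does not carry the phrase. The documents also do not say whether the pilot g values are within-group or between-group, so the bearing of 0.76 on the primary PTSD comparison cannot be judged.

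**Conclusion.** Two small corrections are warranted.

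First, f² = 0.28 is presented as the detectable effect of condition but is too large for the simple 1-df treatment test: about 0.17 at N = 48 and 0.14 at N = 60 before clustering, or 0.19 to 0.20 at N = 48 under an assumed ICC of 0.05 to 0.10. Those values rest on a two-sided test, and the clustered ones also on an assumed group size of 6. Only a large unstated clustering allowance would give 0.28 on 1 df. Read as the treatment test, the error understates what the trial can detect, so it is no evidence that 30 per arm is too few.

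Second, the claim of a clear margin below the pilot effects fails at the low end for the post-treatment comparison. It is reasonable for d = 0.60, and true against g = 3.22.

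The severity is minor. The arithmetic for the 1-df test and the margins is firm; the origin of 0.28 is unknown.

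**What to change.** (a) Replace 0.28 with the two-sided 1-df partial f² for treatment against waitlist at 24 analysed per arm: 0.17 before clustering, with the clustered value and its assumed ICC beside it (0.19 at 0.05, 0.20 at 0.10). Alternatively, keep 0.28 but label it with the test, df and N it came from, and not as the effect of condition.

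(b) Restate the post-treatment d for 24 analysed per arm, giving sidedness, assumed baseline correlation and ICC. Two-sided examples: 0.83 unadjusted; 0.72 at r = 0.5 without clustering; 0.75 to 0.78 at r = 0.5 with ICC 0.05 to 0.10. Both r and ICC are assumptions for the sponsor to justify.

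(c) Reword the pilot comparison to say that the post-treatment detectable effect is close to the lowest pilot effect (g = 0.76) and that the repeated-measures figure (d = 0.60) is below it. Name the outcome and contrast behind 0.76.

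The cost is a text change, with no extra participants and no change to design or analysis. The downside is a less favourable stated margin over the pilot effects.

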Predictor Variables: Predictor is treatment (Islamic Trauma Healing vs. WL)

Dependent Variables: Negative beliefs (PTCI), connectedness (SC; DSES), and forgiveness (TRIM-R) will be measured.

Analyses: We will conduct similar analyses to Aim 1, using both GLMs and GLMMs to obtain effect size estimates. In the GLMs, treatment will predict negative beliefs, connectedness, and forgiveness from baseline to post-treatment (controlling for baseline levels). GLMMs will be conducted as above, and treatment will be used to predict post-treatment levels and change over time in the dependent variables, to estimate how groups

STUDY PROTOCOL: A Lay-Led Intervention for War and Refugee Related Trauma: NCT03502278
July 18, 2018

differ in their rate of symptom reduction over the course of treatment.

Exploratory Hypothesis. Changes in negative beliefs (PTCI), connectedness (SC; DSES), and/or forgiveness (TRIM-R) will mediate the relationship between treatment condition and changes in PTSD and related symptoms. For the GLMs, we will predict Session 3 mediators from treatment (a path) and follow-up outcomes from the mediator (b path) controlling for treatment and baseline levels. Mediation will be tested using the product of coefficients method with bootstrapped standard errors (MacKinnon et al., 2009). In the GLMMs, we will conduct a 2-1-1 mediation, predicting the mediator at all time points from treatment (2-1), and the outcome at all time points from the mediator (1-1), controlling for treatment. This will be based on Bauer et al. (2006), generally following the product of coefficients method. It is recognized that this is underpowered.

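### Two conflicting rules are given for therapy-group nesting, dummy codes and random intercepts; neither is said to govern, and the dummy rule, the only one reaching the GLMs, has no stated coding

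*Combined protocol and SAP*

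**What the plan says.** Section G (Analytic Strategy) deals with participants nested in therapy groups in the active arm by fixed covariates: "we will co-vary treatment group using dummy codes in all analyses, as linear mixed models are difficult to estimate". Its reason is that such models are "difficult to estimate when the number of clusters is very small".

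The Specific Aim 1 analyses treat the same nesting differently: "we will include random intercepts for both treatment group and cluster (for those choosing to be randomized in a cluster". These intercepts apply only to people in a therapy group or a randomisation cluster. The models are meant "to estimate the effects of treatment on both the level of the outcome at post-treatment, as well as change over time".

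Specific Aim 2 uses two model families: "We will conduct similar analyses to Aim 1, using both GLMs and GLMMs to obtain effect size estimates". For the mixed models it refers back: "GLMMs will be conducted as above". For the others it says only: "In the GLMs, treatment will predict negative beliefs, connectedness, and forgiveness from baseline to post-treatment (controlling for baseline levels". The exploratory hypothesis adds a mediation GLM, with this test: "Mediation will be tested using the product of coefficients method with bootstrapped standard errors". Neither the Aim 2 GLMs nor the mediation GLM has a therapy-group rule of its own.

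**The concern.** The two rules cover the same source of dependence and cannot usefully be combined: once every therapy group has a fixed dummy, the therapy-group random intercept has nothing left to estimate. No sentence ranks them or makes one a fallback, and the reason given for the first argues against the second. Analysts following one or the other can report different estimates, standard errors and p-values for the primary outcome, and the choice could be made after seeing results.

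The GLMs have a further problem. Therapy groups exist only in the active arm, so what a group dummy does to the treatment coefficient depends on the coding, and none is stated.

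**Working it through.** **Inputs.** 30 per arm (sections A and F). Therapy groups of 5-7 members (section B). Since 30/7 = 4.3 and 30/5 = 6, I assume 5 groups of 6 or 6 groups of 5. The documents give neither the number of groups nor an intraclass correlation (ICC), so ICC = 0 to 0.20 is an assumed range. SD = 1, two-sided 0.05.

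**Benchmark.** The plan's d = 0.72: (1.960 + 0.842) × √(2/30) = 2.802 × 0.2582 = 0.72. This reproduces it two-sided with 30 per arm and no dropout. It serves only as a yardstick here; the point does not depend on it.

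**Coding 1: a dummy for every group, beside treatment.** The dummies sum to the treatment indicator.

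| Model | Columns | Rank |
|---|---|---|
| 5 groups | 7 | 6 |
| 6 groups | 8 | 7 |
| 5 groups + baseline | 8 | 7 |
| 6 groups + baseline | 9 | 8 |
| 5 groups, time and treatment × time | 9 | 8 |

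The treatment main effect and the post-treatment level are not estimable. In the last model treatment × time is estimable.

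**Coding 2: one dummy dropped.** The treatment coefficient becomes the omitted group (m people) against the whole waitlist, with SE = √(1/m + 1/30):

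- m = 5: √(0.2000 + 0.0333) = 0.48
- m = 6: √(0.1667 + 0.0333) = 0.45
- m = 7: √(0.1429 + 0.0333) = 0.42
- both full arms: √(2/30) = 0.26

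Power at d = 0.72 (noncentral t) is 31-39%, against 78% for the two-arm contrast. The Aim 2 GLMs adjust for baseline. With an assumed baseline correlation of 0.5, each SE is multiplied by √(1 − 0.25) = 0.866, and power is 39-49% against 89%.

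**Coding 3: averaged or centered dummies.** The average treatment effect is estimable, but the reported SE leaves out between-group variance. For k groups of m:

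- reported SE ≈ √[1/30 + (1 − ICC)/30]
- SE for inference beyond the groups run = √[1/30 + (1 − ICC)/30 + ICC/k]

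With 5 groups of 6 these are 0.255 and 0.274 at ICC 0.05, 0.252 and 0.289 at 0.10, and 0.245 and 0.316 at 0.20. Simulated type I error for that wider inference:

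| ICC | 5 groups of 6 | 6 groups of 5 |
|---|---|---|
| 0 | 5% | 5% |
| 0.05 | 6.8% | 6.5% |
| 0.10 | 8.5% | 7.9% |
| 0.20 | 12.4% | 11.2% |

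**Is section G's small-cluster worry real?** Yes. The chance that restricted maximum likelihood estimates the group variance as zero is P[F(k−1, k(m−1)) < (1 − ICC)/(1 + (m−1)ICC)]. With 5 groups of 6 this is 44%, 33% and 19% at ICC 0.05, 0.10 and 0.20.

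**Price of the random-intercept model.** Detectable d = 2.802 × √[(1 + 5·ICC)/30 + 1/30] = 0.77, 0.81 and 0.89 at ICC 0.05, 0.10 and 0.20 (5 groups of 6, normal approximation, no dropout).

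**The case against.** The best defence is that the Aim 1 text is specific and section G is general, so a sensible analyst would follow Aim 1. That model is workable, the Aim 2 GLMMs inherit it, and both hypotheses concern greater reduction, which treatment × time can test even with main-effect dummies. Much of this stands. A reader might infer that aliasing destroys the primary analysis; the documents do not support that, because Aim 1 has its own adequate model. But they state no specific-over-general rule, and section G's wording exempts nothing.

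Second, a full dummy set is visibly rank-deficient, so software would warn or drop a column, and dummies with waitlist as reference, then averaged, do give a treatment effect. That also stands. A reader might infer that dummy coding always makes treatment inestimable; it does so only under one coding, and none is stated. Inference limited to the groups run is a defensible target if declared, but the plan does not declare it. The inflation figures rest on assumed ICCs and vanish at zero.

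Third, one might say that only the Aim 2 GLMs lack an alternative. That is too narrow: section F quotes an effect size for GLMs, and Aim 2 describes its GLMs and GLMMs as similar to Aim 1, so Aim 1 GLMs are implied but nowhere specified.

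Finally, a reader might infer that therapy-group clustering invalidates the planned bootstrap. The evidence does not support this. The simulations used percentile intervals, whereas the plan names bootstrapped standard errors, and percentile intervals already rejected about 7-9% at ICC 0.

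**Conclusion.** The contradiction is real and needs correcting before analysis. For Aim 1, including the primary outcome, and for the Aim 2 GLMMs, it is an unresolved choice between two rules, one of which works. For the Aim 2 GLMs, the mediation a path and any implied Aim 1 GLM, the dummy rule is the only stated therapy-group adjustment. Depending on an unstated coding it gives no treatment coefficient, a one-group contrast with SE 1.6 to 1.9 times too large for the two-arm comparison (0.42/0.26 to 0.48/0.26), or an SE valid only for the groups run. The rank result follows from the design alone. The other sizes assume 30 per arm, 5 or 6 groups, the ICC range above and, for adjusted power, a baseline correlation of 0.5.

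**What to change.** Delete the dummy-code sentence in section G and state that the Aim 1 partially nested model governs Aims 1 and 2, with Satterthwaite or Kenward-Roger degrees of freedom where the model is linear.

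Because the small-cluster worry is sound, name a fallback for non-convergence. One example is therapy-group means against waitlist randomisation-unit means with Satterthwaite degrees of freedom (simulated type I error 5.1-5.5% with waitlist units of one person, 4.9-5.1% with units of one to three).

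For the GLMs, use the same model, or small-sample-corrected (CR2) cluster-robust SEs, with the therapy group as cluster in the active arm and the randomisation unit as cluster in the waitlist. Simulated type I error was about 4.3-5.9%, assuming randomisation units lie within therapy groups, which the documents do not say. If dummies are kept anywhere, specify centered codes and state that inference is limited to the groups run. Base the a-path uncertainty in the exploratory mediation on the same model; further rules for the bootstrap are optional.

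The cost is wording plus intervals wider than under averaged dummies, a width the Aim 1 model already carries. With 5 groups of 6, detectable d rises from 0.72 to about 0.77, 0.81 and 0.89 at assumed ICC 0.05, 0.10 and 0.20. With t reference distributions it rises from 0.74 to 0.84, 0.89 and 1.00. Dropout is not counted in these figures.
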